17.1. Reportable Events by Investigational Site to Boston Scientific

It is the responsibility of the investigator to assess and report to BSC any event which occurs in any of following categories:

- All Serious Adverse Events
- All Study Device, Study Procedure, and Study Procedure Anesthesia-related Adverse Events
- All Investigational Device Deficiencies
- Unanticipated Adverse Device Effects
- New findings/updates in relation to already reported events

When possible, the medical diagnosis should be reported as the Event Term instead of individual symptoms.

If it is unclear whether or not an event fits one of the above categories, or if the event cannot be isolated from the device, procedure, or anesthesia, it should be submitted as an adverse event and/or device deficiency.

Any AE event required by the protocol, experienced by the study subject after informed consent and once considered enrolled in the study (as defined in study subject classification section), whether during or subsequent to the procedure, must be recorded in the eCRF.

Underlying diseases are not reported as AEs unless there is an increase in severity of frequency during the course of the investigation. Death should not be recorded as an AE, but should only be reflected as an outcome of one (1) specific SAE (see Table 17.2-1 for AE definitions).

Refer to Section 16 for the known risks associated with the study device(s).

Adverse event definitions are provided in Table 17.1-1. Administrative edits were made to combine definitions from ISO 14155-2011 and MEDDEV 2.7/3 12/2010.

Table 17.1-1: Safety Reporting Definitions

Term	Definition
Adverse Event (AE) Ref: ISO 14155-2011 Ref: MEDDEV 2.7/3 12/2010	Any untoward medical occurrence, unintended disease or injury, or any untoward clinical signs (including an abnormal laboratory finding) in subjects, users or other persons, whether or not related to the investigational medical device. NOTE 1: This includes events related to the investigational medical device or comparator. NOTE 2: This definition includes events related to the procedures involved (any procedure in the clinical investigation plan).

Table 17.1-1: Safety Reporting Definitions

Term	Definition
	NOTE 3: For users or other persons, this definition is restricted to events related to the investigational medical device.
Adverse Device Effect (ADE) Ref: ISO 14155-2011 Ref: MEDDEV 2.7/3 12/2010	Adverse event related to the use of an investigational medical device NOTE 1: This definition includes any adverse event resulting from insufficient or inadequate instructions for use, the deployment, the implantation, the installation, the operation, or any malfunction of the investigational medical device. NOTE 2: This definition includes any event resulting from use error or from intentional misuse of the investigational medical device.
Serious Adverse Event (SAE) Ref: ISO 14155-2011 Ref: MEDDEV 2.7/3 12/2010	Adverse event that: 
• Led to death,• Led to serious deterioration in the health of the subject, that either resulted in:
◦ a life-threatening illness or injury, or◦ a permanent impairment of a body structure or a body function, or◦ in-patient or prolonged hospitalization of existing hospitalization, or◦ medical or surgical intervention to prevent life-threatening illness or injury or permanent impairment to a body structure or a body function• Led to fetal distress, fetal death, or a congenital abnormality or birth defect. NOTE 1: Planned hospitalization for a pre-existing condition, or a procedure required by the clinical investigational plan, without serious deterioration in health, is not considered a serious adverse event.
Serious Adverse Device Effect (SADE) Ref: ISO 14155-2011 Ref: MEDDEV 2.7/3 12/2010	Adverse device effect that has resulted in any of the consequences characteristic of a serious adverse event.
Unanticipated Adverse Device Effect (UADE) Ref: 21 CFR Part 812 Note: For US IDE studies only, otherwise remove UADE from table	Any serious adverse effect on health or safety or any life-threatening problem or death caused by, or associated with, a device, if that effect, problem, or death was not previously identified in nature, severity, or degree of incidence in the investigational plan or application (including a supplementary plan or application), or any other unanticipated serious problem associated with a device that relates to the rights, safety, or welfare of subjects.
Device Deficiency Ref: ISO 14155-2011 Ref: MEDDEV 2.7/3 12/2010	A device deficiency is any inadequacy of a medical device with respect to its identity, quality, durability, reliability, safety or performance. NOTE 1: Device deficiencies include malfunctions, misuse or use errors, and inadequate labeling.

Table 17.1-1: Safety Reporting Definitions

Term	Definition

Abbreviations: EC=Ethics Committee; IRB=Institutional Review Board

Underlying diseases are not reported as AEs unless there is an increase in severity or frequency during the course of the investigation. Death should not be recorded as an AE, but should only be reflected as an outcome of a specific SAE (see Table 17.1-1 for AE definitions).

Any related AE experienced by the study subject after informed consent, whether during or subsequent to the procedure, must be recorded in the eCRF.

Refer to Section 16 for the known risks associated with the study device(s).

17.2. Relationship to Study Device(s)

The Investigator must assess the relationship of the AE to the study device, study procedure, or study procedure anesthesia as related or not related. See criteria in Table 17.2-1:

Table 17.2-1: Criteria for Assessing Relationship of Study Device, Study Procedure, & Study Procedure Anesthesia to Adverse Event

Classification	Description
Not Related	The adverse event is determined to be due to a concurrent illness or effect of another device/drug and is not related to the investigational product.
Related	
 The adverse event is determined to be potentially related to the investigational product, and an alternative etiology is equally or less likely compared to the potential relationship to investigational product, or There is a strong relationship to investigational product, or recurs on re-challenge, and another etiology is unlikely, or There is no other reasonable medical explanation for the event.

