2.4. Medical Equipment Description

In addition to the iNod System, all pulmonary endoscopy, or surgical suites where the study procedure is being performed must also be equipped with:

- 2.0 mm working channel bronchial scope model numbers Olympus BF-P190 or Olympus BF-MP160F
- Fluoroscopy
- All equipment necessary for Radial EBUS-guided biopsy of peripheral pulmonary lesions.
- Cytological Rapid On-Site Evaluation (ROSE)

All research centers are also required to have on-site capabilities for Chest X-Ray.

3. Objectives

To demonstrate feasibility to access, visualize, and obtain specimens adequate for cytology of lung lesions in subjects with suspected lung cancer when using the iNod System.

4. Endpoints

Primary Endpoint:

Clinical success is defined as the iNod System's ability to acquire adequate specimens of cellular matter suitable for the cytologic evaluation of targeted lung lesions, under real-time visualization.

Salvage Procedure: In case of primary endpoint failure with the iNod System, Radial EBUS -guided diagnostic sampling maneuvers (current standard-of-care) will be performed in an attempt to access, visualize, and sample targeted lung lesions.

Secondary Endpoints:

- 1) Occurrence and severity of Adverse Events related to the iNod System biopsy procedures, as well as Adverse Events related to any subsequent Radial EBUS-guided salvage procedures.
- 2) Proportion of lesions visualized during iNod Maneuvers
- 3) Proportion of lesions accessed where iNod Biopsy Needles were deployed during study maneuvers
- 4) Proportion of iNod maneuvers that acquire specimens of cellular matter for cytology

5. Design, Scale, and Duration

This study is a multi-center, prospective, single-arm human feasibility assessment.

Treatment of 15-30 subjects will take place at 2-3 clinical centers. No single clinical center will enroll in excess of 10 subjects. As the iNod System is being evaluated as a diagnostic system, study subjects are expected to be consented no more than 2 weeks prior to or up to and including the day of, but prior to, their diagnostic procedure. Subjects will exit the study, post-procedure following a pre-discharge x-ray. In the case of occurrence of a procedure-related Adverse Event, the subject will be followed through event resolution.

6. Subject Selection

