Imaging to be captured during the iNod System maneuvers, as identified with the serial number of the iNod Imaging System and iNod Biopsy Needle being utilized for each maneuver, will be collected as follows:

- Ultrasound image of the target lesion
- Ultrasound image of the deployed iNod Biopsy Needle at the target lesion
- Supplemental fluoroscopic images, if collected, should also be retained and similarly associated to the specific maneuver by documenting the serial number of the iNod Biopsy Needle being used for that specific procedure

Rapid on-site evaluation (ROSE) will be completed for all obtained specimens. Results will be associated with the serial number of the iNod Biopsy Needle being used for each unique specimen. ROSE interpretations, “adequate (for cytologic evaluation)” or “inadequate (for cytologic evaluation),” will be recorded. Collected specimens will undergo cytologic evaluation following the iNod procedure and final cytologic results will be reported in the study database.

The following situations would indicate the need to abandon the iNod System Procedure and proceed to salvage:

- If the iNod System is unable to physically reach the lesion, as evidenced by the absence of an ultrasound image of the lesion with the iNod System.
- If 3 separate aspirated specimens obtained from the target lesion with the iNod System result in “inadequate (for cytologic evaluation),” the investigator should stop iNod maneuvers and proceed to salvage.

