8.6. Salvage Procedure

For study subjects for whom an adequate specimen, defined as a specimen that has been confirmed as suitable for cytologic evaluation, is not obtained from the iNod System diagnostic procedure but for whom continuation with endobronchial maneuvers are not contraindicated, additional standard of care (SOC) R-EBUS-guided diagnostic sampling maneuvers should be conducted.

SOC R-EBUS-guided sampling maneuvers may be conducted utilizing various clinically standard sampling techniques, including but not limited to fine-needle aspiration, brushings, or forceps. Similar to the iNod System procedure, accountability of all SOC devices utilized, timing, ultrasound image(s) of target lesion, fluoroscopic images of lesions and sampling device, as available, ROSE, and Final Cytology should be captured.

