3 GENERAL STATISTICAL METHODS

3.1 Description of Statistical Methods

Descriptive statistics will be presented for all intent-to-treat (ITT) and per-protocol (PP) patients. The mean (\pm standard deviation) will be used to describe continuous variables with a normal distribution and the median (and interquartile range) will be used to describe continuous variables with a skewed distribution. Frequency tables will be used to summarize discrete variables. Proportions of patients with adverse events and SAEs will be reported. No hypothesis testing will be performed.

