3.2 Analysis Sets

3.2.1 Intent-to-Treat Cohort

The intent-to-treat (ITT) cohort consists of subjects enrolled in the study regardless of whether a specimen was obtained from the iNod System. The point of enrollment is the time at which, following recruitment, a subject signs and dates the informed consent form.

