3.2.2 Per Protocol Cohort

The per-protocol (PP) cohort is a subset of the ITT subjects for whom a specimen was obtained using the iNod System.

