6.3 Rules and Definitions for Calculated Variables

The following sections describe the identification of the ITT and PP patients and the calculation of the primary endpoint of clinical success.

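### Secondary endpoint 1 covers AEs related to iNod and AEs related to R-EBUS salvage, but the stated relationship rule and AE analysis do not deliver that split

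*Protocol*

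**What the plan says.** **Endpoint.** Protocol Section 4, the synopsis and SAP 4.1 all define secondary endpoint 1 as the occurrence and severity of AEs related to the iNod biopsy procedures, "as well as Adverse Events related to any subsequent Radial EBUS-guided salvage procedures".

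**Relationship rule.** The lead sentence of Protocol 17.2 and the title of Table 17.2-1 name three axes: study device, study procedure and study procedure anesthesia. The criteria inside the table are narrower. An event is Not Related if it is "due to a concurrent illness or effect of another device/drug and is not related to the investigational product". The first two bullets under Related also test only the investigational product, and the third names no target.

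**Salvage.** Protocol 8.5 gives two routes to salvage. The first is worded "If the iNod System is unable to physically reach the lesion", shown by the absence of an iNod ultrasound image of it. The second is three inadequate aspirates. Under 8.6 the salvage tools are standard-of-care ones, "including but not limited to fine-needle aspiration, brushings, or forceps".

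**Analysis.** SAP 3.1 states that "Proportions of patients with adverse events and SAEs will be reported", with descriptive statistics for ITT and PP. ITT is "subjects enrolled in the study regardless of whether a specimen was obtained from the iNod System", with enrollment at signature of the consent form. PP is a "subset of the ITT subjects for whom a specimen was obtained using the iNod System". SAP 6.3 introduces its derivation rules as covering "the identification of the ITT and PP patients and the calculation of the primary endpoint of clinical success"; it also adds a restricted PP cohort. It has no rule for AE relatedness or for an AE denominator.

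**The concern.** A subject in whom iNod fails can have both procedures in one bronchoscopy session. In Protocol 16.1, 11 anticipated event terms are marked as specific to iNod and similar standard-of-care devices, pneumothorax and bleeding among them. The type of event therefore does not show its source.

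The endpoint still asks for events by source. If the relationship criteria recognize only the investigational product, or a single procedure field covers the whole session, the salvage part cannot be read off the relationship assessment. The planned proportions do not help, because neither main analysis set is the group exposed to iNod or the group exposed to salvage. At stake is the interpretability of the safety endpoint in a first human use of the system.

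**Working it through.** The documents give no AE rate or salvage rate, so there is no planned figure to reproduce. The check is mainly textual, with arithmetic to show scale.

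**Step 1: what the rule yields for an event caused by salvage forceps.**
- *Criteria read literally.* The forceps are another device and the event is not related to iNod. Both halves of the Not Related text are met, so the event is Not Related. The endpoint needs it counted as salvage-related.
- *Title and lead sentence govern, and study procedure means the whole session.* The event is Related (procedure). So is an event caused by manipulating the iNod needle, and one field now holds both.
- *Study procedure means the iNod procedure only.* Salvage has no axis.

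None of the three readings gives the endpoint's two parts.

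**Step 2: the denominators.** Let A be the subjects in whom iNod was attempted, c those consented but never instrumented, and u those attempted with no iNod specimen.
- ITT = A + c. Protocol 7.2 lets subjects withdrawn before the procedure fall outside a center's 10-subject limit, so c can exceed zero. The rate x/(A + c) is then below x/A.
- PP = A − u. Subjects salvaged because the lesion was not reached have no iNod specimen and fall in u. Those salvaged after three inadequate aspirates did give a specimen and stay in PP. PP therefore keeps one salvage route and loses the other.
- Example (assumption: A = 15, u = 3, and the only AE occurs in one of those three). The attempted-subject rate is 1/15 = 6.7%. PP has 15 − 3 = 12 subjects and shows 0/12 = 0%.

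**Step 3: effect of one salvage event on the source-specific rates.** Inputs: 15 to 30 treated subjects (Protocol Section 5) and an assumed salvage share of 20% to 50%. That gives 0.20 × 15 = 3 up to 0.50 × 30 = 15 salvaged subjects. The affected subject is assumed to have no other event from the source in question.

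| Quantity | Smallest case | Largest case |
|---|---|---|
| iNod rate, if the event is credited to iNod | +1/15 = 6.7 points | +1/30 = 3.3 points |
| Salvage rate, if the event is called Not Related or credited to iNod | −1/3 = 33.3 points | −1/15 = 6.7 points |
| Exact 95% CI, event counted as salvage | 1/3: 0.8% to 90.6% | 1/15: 0.2% to 31.9% |
| Exact 95% CI, event not counted as salvage | 0/3: 0% to 70.8% | 0/15: 0% to 21.8% |

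The iNod row needs no assumed salvage share, but the other rows do. The intervals overlap widely, so even a correctly attributed salvage rate would be imprecise. In every case the overall AE count is unchanged.

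**The case against.** The other side has real points.

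- The title and lead sentence of Table 17.2-1 do name procedure and anesthesia, so the criteria may be template text meant to be applied along each axis. The synopsis describes the bronchoscopy procedure as iNod sampling followed by salvage where needed, which favors placing salvage under procedure. That would stop salvage events being called Not Related, but it would still merge them with iNod events.
- Endpoint 1 speaks of occurrence and severity, whereas endpoints 2 to 4 speak of proportions. Counts or listings by source would satisfy it. SAP 3.1 also allows frequency tables and SAP 6.2 allows listings. This stands: a rate is not required. No by-source table or listing is stated, however, and the AE proportions that are stated use unsuitable denominators.
- Procedure worksheets record devices and timing for both kinds of maneuver, the Medical Monitor evaluates safety events, and the sponsor has access to source. With at most 30 subjects, many events could be assigned by case review. This limits the harm but is not a rule.

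A reader might infer more than the documents support:

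- *That salvage AEs would go unrecorded.* The reportable list in 17.1 takes in all SAEs and all study-procedure-related events. The same section tells sites to submit events whose source is unclear or cannot be isolated, the AE definition covers any procedure in the plan, and 14.2 asks investigators to record every AE. The weight of the text is toward capture.
- *That the AE form lacks a salvage field.* Table 17.3-1 gives only examples of its content, and the form is not in the documents.
- *That the SAP ignores the endpoint.* SAP 4.1 lists it; what is missing is the method.

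**Conclusion.** The point holds as a gap in attribution and analysis. The relationship axes do not separate iNod from salvage, the criteria read literally put salvage-tool events under Not Related, and the stated AE proportions use one set that can be diluted and another that is selectively incomplete.

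The size is modest. One misattributed event moves the iNod rate by 3.3 to 6.7 points. The 6.7 to 33.3 point shift in a salvage rate rests on an assumed 20% to 50% salvage share and is illustrative. No hypothesis or threshold depends on the split. The plan should be corrected because the endpoint is the study's safety endpoint and the correction is cheap, not because any planned result is invalid.

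**What to change.** **Protocol 17.2.** Reword Table 17.2-1 so that each criterion applies to the named source. State whether study procedure includes salvage. Record relationship separately to iNod, to R-EBUS salvage and to anesthesia, adding AE form fields only if they are absent.

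**SAP 4.1.** Tabulate or list AEs with severity by source, using iNod-attempted subjects as the denominator for iNod events and salvaged subjects for salvage events. Flag events that cannot be separated and show them beside the overall total.

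**Cost.** Protocol and SAP wording, one table or listing and, at most, one or two form fields. No added visit or subject. If inseparable events are shown under both sources, the source counts can exceed the total, which is why the total must stand next to them.

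**Separate item.** Protocol Section 5 has subjects exit after the pre-discharge x-ray, while the synopsis, Table 8.1-1, Section 8.7 and the SAP summary include a Day 7 call. Those passages must be reconciled, but this concerns the AE window rather than attribution.

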17.3. Investigator Reporting Requirements

The communication requirements for reporting to BSC are as shown in Table 17.3-1.

Table 17.3-1: Investigator Reporting Requirements

Event Classification	Communication Method	Communication Timeline
Unanticipated Adverse Device Effect	Complete AE eCRF page with all available new and updated information.	
 Within 1 business day of first becoming aware of the event. Terminating at the end of the study

Table 17.3-1: Investigator Reporting Requirements

Event Classification	Communication Method	Communication Timeline
Serious Adverse Event including Serious Adverse Device Effects	Complete AE eCRF page with all available new and updated information.	
 • Within 2 business days of first becoming aware of the event or as per local/regional regulations. • Reporting required through the end of the study
	Provide all relevant source documentation (unidentified) for reported event	
 • When documentation is available
Device Deficiencies (including but not limited to failures, malfunctions, and product nonconformities) Note: Any Investigational Device Deficiency that might have led to a serious adverse event if a) suitable action had not been taken or b) intervention had not been made or c) if circumstances had been less fortunate is considered a reportable event.	Complete Device Event Form	
 • Within 2 business days of first becoming aware of the event and as per local/regional regulations. • Reporting required through the end of the study
Adverse Event	Complete AE eCRF page, which contains such information as date of AE, treatment of AE resolution, assessment of seriousness and relationship to the device.	
 • In a timely manner (e.g. Recommend within 10 business days) after becoming aware of the information • Reporting required through the end of the study

Abbreviations: AE=adverse event; CRF=case report form; IDE=Investigational Device Exemption;
UADE=unanticipated adverse device effect

17.4. *Boston Scientific Device Deficiencies*

All device deficiencies (including but not limited to failures, malfunctions, use errors, product nonconformities, and labeling errors) will be documented and reported to BSC. If possible, the device(s) should be returned to BSC for analysis. Instructions for returning the investigational device(s) will be provided. If it is not possible to return the device, the investigator should document why the device was not returned and the final disposition of the device. Device failures and malfunctions should also be documented in the subject's medical record.

Device deficiencies (including but not limited to failures, malfunctions, and product nonconformities) are to be reported as Device Events and are not to be reported as

adverse events. However, if there is an adverse event that results from a device failure or malfunction, that specific event would be recorded on the Adverse Event eCRF.

Any Investigational Device Deficiency that might have led to a serious adverse event if a) suitable action had not been taken or b) intervention had not been made or c) if circumstances had been less fortunate is considered a reportable event.

17.5. *Reporting to Regulatory Authorities / IRBs / ECs / Investigators*

BSC is responsible for reporting adverse event information to all participating investigators and regulatory authorities, as applicable.

The Principal Investigator is responsible for informing the IRB/EC, and regulatory authorities of UADE and SAE as required by local/regional regulations.

18. Informed Consent

Subject participation in this clinical study is voluntary. Informed Consent is required from all subjects or their legally authorized representative. The Investigator is responsible for ensuring that Informed Consent is obtained prior to the use of any investigational devices, study-required procedures and/or testing, or data collection.

The obtaining and documentation of Informed Consent must be in accordance with the principles of the Declaration of Helsinki, ISO 14155, any applicable national regulations, and local Ethics Committee and/or Regulatory authority body, as applicable. The ICF must be approved by BSC or its delegate (e.g. CRO), the center's IRB/EC, or central IRB, if applicable.

Boston Scientific will provide a study-specific template of the ICF to investigators participating in this study. The ICF template may be modified to meet the requirements of the investigative center's IRB/EC. Any modification requires approval from BSC prior to use of the form. The ICF must be in a language understandable to the subject and if needed, BSC will assist the center in obtaining a written consent translation. Translated consent forms must also have IRB/EC approval prior to their use. Privacy language shall be included in the body of the form or as a separate form as applicable.

The process of obtaining Informed Consent shall at a minimum include the following steps, as well as any other steps required by applicable laws, rules, regulations and guidelines:

- be conducted by the Principal Investigator or designee authorized to conduct the process,
- include a description of all aspects of the clinical study that are relevant to the subject's decision to participate throughout the clinical study,
- avoid any coercion of or undue influence of subjects to participate,
- not waive or appear to waive subject's legal rights,

- use native language that is non-technical and understandable to the subject or his/her legal representative,
- provide ample time for the subject to consider participation and ask questions if necessary,
- ensure important new information is provided to new and existing subjects throughout the clinical study.

The ICF shall always be signed and personally dated by the subject or legal representative competent to sign the ICF under the applicable laws, rules, regulations and guidelines and by the investigator and/or an authorized designee responsible for conducting the informed consent process. If a legal representative signs, the subject shall be asked to provide informed consent for continued participation as soon as his/her medical condition allows. The original signed ICF will be retained by the center and a copy of the signed and dated document and any other written information must be given to the person signing the form.

Failure to obtain subject consent will be reported by BSC to the applicable regulatory body according to their requirements (e.g., FDA requirement is within 5 working days of learning of such an event). Any violations of the informed consent process must be reported as deviations to the sponsor and local regulatory authorities (e.g. IRB/EC), as appropriate.

If new information becomes available that can significantly affect a subject's future health and medical care, that information shall be provided to the affected subject(s) in written form via a revised ICF or, in some situations, enrolled subjects may be requested to sign and date an addendum to the ICF. In addition to new significant information during the course of a study, other situations may necessitate revision of the ICF, such as if there are amendments to the applicable laws, protocol, a change in Principal Investigator, administrative changes, or following annual review by the IRB/EC. The new version of the ICF must be approved by the IRB/EC. Boston Scientific approval is required if changes to the revised ICF are requested by the center's IRB/EC. The IRB/EC will determine the subject population to be re-consented.

19. Safety Monitoring Process

To promote early detection of safety issues, the BSC Medical Monitor will provide evaluations of safety events. Success of this program requires dynamic collection of unmonitored data as soon as the event is reported. This is expedited through BSC's Global Safety Office, which is responsible for coordinating the collection of information for the subject dossier from the centers and core laboratories. During regularly scheduled monitoring visits, clinical research monitors will support the dynamic reporting process through their review of source document information.

20. Suspension or Termination

